Efficacy of Laser Debridement on Pain and
Bacterial Load in Chronic Wounds
(NCT03182582)

Study Protocol

November 5, 2015

[name], Principal Investigator
Stanford University
Stanford, California 94305

PROTOCOL SYNOPSIS

Title	The assessment of bio-burden reduction and procedural pain after chronic ulcer debridement.
Sponsor	Sciton, Inc. [name] [contact]
Clinical site	Stanford Advanced Wound Care Center [name] [contact]
Rationale	Chronic ulcers are a significant source of morbidity and pain. Biofilms are present in all chronic ulcer types. Additional methods for safe, effective, and tolerable chronic ulcer bed debridement are needed.
Study design	Randomized-controlled cross over, open label study
Primary objective	To determine the efficacy of the reduction of bioburden in chronic ulcers after laser and sharp debridement.
Secondary objectives	To determine the tolerability of laser and sharp debridement of chronic ulcers.
Number of subjects	Twenty
Subject selection inclusion criteria	
 • Aged eighteen years or older • Having a non-healing chronic ulcer of any etiology present for at least four weeks • Willing and able to adhere to protocol requirements • Signed Informed Consent Form prior to any study related procedure
Subject selection exclusion criteria	
 • Any unstable medical condition • Documented medical history of any significant disease or condition • Documented medical history of immunosuppression • Receiving dialysis • Having osteomyelitis • Pregnancy • Participation in another clinical study involving ulcers within thirty days prior to enrollment
Control treatment	Sharp (scalpel or curette) debridement with standard of care
Test treatment	Laser debridement with standard of care
Duration of subject participation	Subjects will be enrolled in the study for two weeks
Duration of study	The total duration of the study is expected to be six weeks. Recruitment and enrollment: up to four weeks Treatment: two weeks
Prohibited concomitant medications	Current topical or systemic antibiotic therapy
Efficacy evaluations	Significant bioburden reduction as determined by quantitative polymerase chain reaction (PCR) analysis after the debridement procedures.

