The laser provides precise control over the depth of ablation per pass, ranging from twenty five to two hundred microns. Ablation depth is tunable in twenty five-micron increments. The laser system handpiece allows the laser beam to be scanned to form two-dimensional spots onto the pattern size. The range of the pattern size is 0.64 - 9.00 centimeters squared. The handpiece scanner provides complete and uniform application of the laser energy. This application will cover forty percent of the surface within the scanned pattern. An aiming beam, displayed as a red square on the intended treatment surface, allows the clinician to visualize the treatment area. The laser energy will be delivered inside this red square. The adjoining scans will be delivered without gaps or overlaps to ensure even treatment.

Protective eye shields to safeguard against laser light exposures will be provided to the subjects and personnel in treatment room. The eye shields will remain in place until after the completion of the laser treatment. The thermal destruction of tissue creates a smoke by-product. A smoke evacuator attached to the laser handpiece will immediately remove any smoke generated throughout the laser treatment. This removal will prevent the smoke and debris from irritating the ulcer bed.

Laser ablation will be continued until the slough tissue is completely removed. Patient pain and pinpoint bleeding will represent the clinical endpoint of laser debridement. Pinpoint bleeding signifies the laser energy approaching the healthy underlying tissue. Laser debridement will be administered to only slough tissue and ulcer edges. Healthy granulation tissue in the ulcer bed will not be laser treated. After the completion of the laser debridement procedure, sterile gauze will be used to gently clean the ulcer bed to remove any remaining debris.

STUDY SCHEDULE

Screening and Enrollment (Study Week One):

- Obtain signed Informed Consent Form
- Review medical history to determine eligibility
- Perform medical examinations needed to determine eligibility

- Collect ulcer measurements and photos
- Randomize patients to treatment groups
- Provide subjects instructions needed for study participation
- Immediately proceed to the Treatment

Treatment (Study Week One):

1. Before debridement procedure:
 - Record VAS pain score, Present Pain Intensity, and Brief Pain Inventory
 - Collect ulcer photos and measurements
 - Collect biopsies
2. Apply anesthetic

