3. Perform debridement procedure
 - Record technique or laser settings used during treatment
4. After debridement procedure:
 - Collect ulcer photos
 - Record VAS pain score, Present Pain Intensity, and Brief Pain Inventory
 - Record bleeding assessment
 - Collect biopsies
 - Provide Standard of Care

Follow Up Visit (Study Week Two):

- Subjects cross over to other study group
 - Remove ulcer dressing
1. Before debridement procedure:
 - Record VAS pain score, Present Pain Intensity, and Brief Pain Inventory
 - Collect ulcer photos and measurements
 - Collect biopsies
 2. Apply anesthetic
 3. Perform debridement procedure
 - Record technique or laser settings used during treatment
 4. After debridement procedure:
 - Collect ulcer photos
 - Record VAS pain score, Present Pain Intensity, and Brief Pain Inventory
 - Record bleeding assessment
 - Collect biopsies
 - Provide Standard of Care

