Efficacy of Laser Debridement on Pain and Bacterial Load in Chronic Wounds (NCT03182582)

Statistical Analysis Plan

February 6, 2018

[name], Principal Investigator
Stanford University
Stanford, California 94305

Methods:

This is a prospective, randomized, controlled, crossover clinical trial, entailing two groups: 1) one group receiving a single laser debridement session first, followed by a single sharp debridement session one week later; 2) the other group receiving a single sharp debridement session first, followed by a single laser debridement session one week later. Analysis variables include pain during debridement, pre- and post-debridement wound sizes, pre- and post-debridement bacterial loads, and patient preference.

Statistical Analysis:

The a priori power analysis presumes a 50% reduction in patient-reported pain. A sample size of 22 patients would be required to achieve 80% power, using a two-tailed test with $\alpha = 0.05$. Descriptive analyses include means (standard deviation). A paired t-test was planned to evaluate continuous data, and the 3x2 Fisher's exact test was planned to analyze categorical data. For all data analyses performed in the study, $p < 0.05$ is considered statistically significant.

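### Open-label randomization is scheduled before the week-one baseline biopsies and pain scores, so the primary endpoint's baseline can be sampled with the allocation known

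*Protocol*

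**What the plan says.** The Study design row of the Protocol Synopsis describes a "Randomized-controlled cross over, open label study".

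The Study Schedule, Screening and Enrollment (Study Week One), runs in this order: consent, medical history, examinations, "Collect ulcer measurements and photos", "Randomize patients to treatment groups", instructions to the patient, and "Immediately proceed to the Treatment". Step 1 of Treatment (Study Week One), before anesthetic and debridement, then includes "Record VAS pain score, Present Pain Intensity, and Brief Pain Inventory" and "Collect biopsies".

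At the Follow Up Visit (Study Week Two) the first item is "Subjects cross over to other study group", followed by the same pre-debridement block.

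The primary endpoint in the Synopsis compares how well the two modalities lower bioburden, measured by quantitative PCR. The SAP's Methods section lists "pre- and post-debridement bacterial loads" among the analysis variables. For pain, the SAP names only the pain felt while the wound is being debrided. It mentions no baseline pain score and no change from one.

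**The concern.** A baseline that enters the outcome is best fixed before anyone involved knows the assignment. Here the week-one baselines follow an open-label randomization, although nothing in the schedule requires that order.

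The biopsy matters most. The pre-debridement bacterial load is one of the two values that make up each pre-to-post comparison for the primary endpoint. The documents do not say who takes the sample or from which part of the ulcer. The Protocol's Ulcer Debridement section confines laser treatment to slough and the wound margin and spares healthy granulation. Someone who knows that laser comes next therefore knows which tissue will be ablated, and could sample differently without intending to. Because the sample is chosen before the assay, an objective laboratory readout gives no protection. If sampling differs according to the coming treatment, the laser-sharp comparison of bacterial reduction is distorted, and this cannot be put right in the analysis.

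**Working it through.** The plan gives no figure to reproduce on this point. The SAP's power statement concerns pain and does not bear on it. The check is one of sequence, with simple arithmetic on how far reordering would help.

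**Is the allocation open at the week-one baselines?**
- Randomization is in the Screening and Enrollment list; the pain scores and biopsies are in the Treatment list that follows it.
- The study is open label. No step delays disclosure, and nobody who assesses or samples is said to be masked.
- The moment of disclosure is not stated. That the allocation is known at baseline is therefore an inference from these facts, though a natural one.

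**Is the order necessary?**
- The instruction to go straight to treatment puts screening and treatment at the same visit.
- The pre-debridement block is identical for both treatments and precedes the anesthetic, so nothing in it depends on the assignment.
- Ulcer measurements and photos are already taken before randomization. Pain scores and biopsies are the items left without an allocation-free baseline.

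**How many measurements are involved?** Each patient has two procedures, each with a biopsy occasion before and after.
- Pre-debridement occasions at week one: 20 of 2 × 20 = 40 (Protocol), or 22 of 2 × 22 = 44 (SAP).
- As a share of all biopsy occasions: 20 of 4 × 20 = 80, or 22 of 4 × 22 = 88, which is one quarter.

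**How much would reordering remove?** Let reduction = pre − post on the analysis scale. Suppose that knowing the treatment shifts the pre-debridement value by s_L before laser and by s_S before sharp, equally in both weeks. Let b = s_L − s_S, and assume equal sequence groups.
- Current order: in either sequence, a patient's laser-minus-sharp difference in reduction is shifted by s_L − s_S = b. The mean bias is b.
- Reordered: a laser-first patient is shifted by 0 − s_S, and a sharp-first patient by s_L − 0. The mean bias is (s_L − s_S)/2 = b/2.
- For assumed b of 0.2, 0.5 and 1.0, the bias falls to 0.1, 0.25 and 0.5.

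The documents support no value for b, nor its sign. If knowledge shifts sampling equally before both treatments, b = 0 and there is no bias under either order.

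**Does the same apply to pain?** If procedural pain is compared directly between treatments, as the Synopsis and SAP wording suggests, a shift in the baseline score contributes 0. It enters only through a change score or a baseline adjustment, and neither is specified.

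**The case against.** The strongest reply is that reordering protects very little. Week two cannot be concealed in a crossover, and the post-procedure pain scores, bleeding assessment and biopsies are unmasked in both weeks. If the worry is where the biopsy is taken, a written sampling-site rule or a masked sampler would cover both biopsies at both visits. This stands: it limits the value of the fix and supports a low severity. It does not justify leaving open the one baseline that can be protected for nothing.

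A second reply is that reordering makes the two weeks unlike: allocation-free baselines in week one, allocation-known in week two. A common shift s confined to week two moves laser-first patients by −s and sharp-first patients by +s. This averages to zero when the sequence groups are equal, and otherwise leaves s(n_SL − n_LS)/n, where n_SL and n_LS are the numbers of sharp-first and laser-first patients. It behaves as an ordinary period effect and is no reason to keep the present order.

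Third, early disclosure is inferred. That is correct. If delayed disclosure was already intended, one sentence in the Protocol would settle the point.

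A reader might also infer that baseline pain scores are biased in favor of laser, since the Protocol anticipates less pain and better biofilm clearance with it. The documents do not support this. No change from baseline pain is defined. Even under change scores, a patient who reports more baseline pain before sharp debridement would show a smaller rise with sharp, which counts against laser. It is true that the schedule records pain only before and after debridement, so the earlier score is the only recorded reference should one be wanted. That makes the baseline score worth protecting, but gives no size or sign to a bias.

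**Conclusion.** The point holds as a low-severity, cheaply corrected weakness of the week-one schedule. It concerns mainly the baseline biopsy behind the primary bacterial-load comparison, at one of each patient's two pre-debridement sampling occasions. Under the assumptions of equal sequence groups and the same effect in both weeks, reordering halves whatever bias arises from baseline sampling with the allocation known. The size and direction of that bias are unknown, and it may be nil.

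The conclusion rests on two assumptions: that the assignment is disclosed when patients are randomized, and that whoever takes the biopsy has some discretion over the site. The documents neither state nor exclude either. They do not show that any baseline was in fact influenced, and they give no basis for a figure in VAS units or for a claim that laser is favored.

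**What to change.** Move "Randomize patients to treatment groups" out of the Screening and Enrollment list and place it after step 1 of Treatment (Study Week One), once the pain scores, photos, measurements and biopsies are complete. Equivalently, keep randomization where it is and state that the allocation is opened only after those entries and samples are done.

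Visits, staff, samples and treatments are unchanged. The one practical cost is that the laser room must be ready before the allocation is known. The safeguard is partial, for the reasons given above. A written sampling-site rule applied at both visits would complement it where reordering cannot reach.

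If patients have already been treated under the present order, the report should state when the allocation was disclosed and whether the person sampling knew it.

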Efficacy of Laser Debridement on Pain and Bacterial Load in Chronic Wounds (NCT03182582)

Statistical Analysis Plan

February 6, 2018

[name], Principal Investigator
Stanford University
Stanford, California 94305

Methods:

This is a prospective, randomized, controlled, crossover clinical trial, entailing two groups: 1) one group receiving a single laser debridement session first, followed by a single sharp debridement session one week later; 2) the other group receiving a single sharp debridement session first, followed by a single laser debridement session one week later. Analysis variables include pain during debridement, pre- and post-debridement wound sizes, pre- and post-debridement bacterial loads, and patient preference.

Statistical Analysis:

The a priori power analysis presumes a 50% reduction in patient-reported pain. A sample size of 22 patients would be required to achieve 80% power, using a two-tailed test with $\alpha = 0.05$. Descriptive analyses include means (standard deviation). A paired t-test was planned to evaluate continuous data, and the 3x2 Fisher's exact test was planned to analyze categorical data. For all data analyses performed in the study, $p < 0.05$ is considered statistically significant.

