Primary endpoint	Comparison of the two treatment modalities to reduce bioburden as determined by quantitative polymerase chain reaction (PCR) analysis, DNA sequencing.
Secondary endpoint	Comparison of the procedural pain from the two treatment modalities as determined by subject reported visual analog scale (VAS) pain scores. Comparison of the procedural bleeding from the two treatment modalities as determined by physician assessment. Procedural bleeding
Other evaluations	Overall subject satisfaction from the two treatment modalities.
Safety evaluations	Incidence of adverse events.
Planned interim analysis	Serious adverse events will be audited by the study team on an ongoing basis throughout the study duration.
Primary statistical analysis plan	Treatment effectiveness will be assessed by a two-sample t-test comparing the evaluation criterion at the two study intervals.
Rationale for number of subjects	This is a pilot study to determine treatment feasibility and efficacy.

SUBJECT INCLUSION CRITERIA

A subject will be eligible for inclusion in this study if ALL of the following criteria apply:

[figure not shown]
- Aged eighteen years or older
- Having an ulcer of any etiology
- Has signed the informed consent form prior to any study protocol related procedure
- Willing and able to adhere to protocol requirements

SUBJECT EXCLUSION CRITERIA

The subject will not be eligible for study inclusion if ANY of the following criteria apply:

- Any unstable medical condition that would cause the study treatment to be detrimental to the subject, as judged by the Principle Investigator
- Documented medical history of significant cardiac, pulmonary, gastrointestinal, endocrine (*other than Diabetes Mellitus type 1 or 2*), metabolic, neurological, hepatic or nephrologic disease would impede the subject's participation, as judged by the Principle Investigator
- Documented medical history of immunosuppression, immune deficiency disorder, or currently using immunosuppressive medications
- Having clinical presentation of active osteomyelitis
- Pregnancy or lactation
- Participation in another clinical study involving ulcers within thirty days prior to enrollment

STUDY DESIGN

ULCER DEBRIDEMENT

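### Does the SAP depend on variables (patient preference, pain during debridement, post-debridement wound size) that the protocol's visit schedule never collects?

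*SAP*

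**What the plan says.** The SAP, Methods, lists the data to be analysed: "Analysis variables include pain during debridement, pre- and post-debridement wound sizes, pre- and post-debridement bacterial loads, and patient preference". Its Statistical Analysis section sizes the study on pain ("The a priori power analysis presumes a 50% reduction in patient-reported pain"), giving 22 patients for 80% power at a two-sided 0.05. It assigns continuous data to a paired t-test. For the rest, a 3x2 Fisher's "exact test was planned to analyze categorical data"; the variable is not named.

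The protocol synopsis gives a secondary endpoint, "Comparison of the procedural pain from the two treatment modalities as determined by subject reported visual analog scale (VAS) pain scores", and under other evaluations, "Overall subject satisfaction from the two treatment modalities". Bioburden is the primary endpoint.

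The Study Schedule has the same sequence at both visits. Before the procedure, three pain instruments (VAS, Present Pain Intensity, Brief Pain Inventory) are recorded, biopsies are taken, and staff are to "Collect ulcer photos and measurements". Next comes the step "Apply anesthetic", then the debridement. Afterwards the same three instruments are recorded, bleeding is assessed and biopsies are repeated, but the imaging step is only "Collect ulcer photos".

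**The concern.** A reader who checks the SAP's list against the schedule finds three mismatches.

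- **Preference** has no step at either visit. Satisfaction, the nearest item, has no instrument or time point. If preference was never asked, no analyst can recover it, and the 3x2 test may have lost its input.
- **Pain** is more prominent, because it is a secondary endpoint and the basis of the sample size. Pain during the procedure, pain once it is over, and change from before are different quantities, and neither document says which one the later VAS captures. Anesthetic is applied between the two scores, so a change score would also carry its effect on existing ulcer pain. An open choice between scores leaves room for selection once results are known.
- **Post-debridement size** has photos behind it but no stated measurement. The pre-debridement measurement at week two cannot stand in: it follows only the first session, and no visit follows the second.

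**Working it through.** **1. Each SAP variable against the Study Schedule**

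| SAP variable | Before debridement | After debridement | Supplied? |
|---|---|---|---|
| Bacterial load | Biopsies, both visits | Biopsies, both visits | Yes |
| Pain during debridement | VAS, both visits | VAS, both visits | Yes, but reference period unstated |
| Wound size | Photos and measurements, both visits | Photos only, both visits | Before yes; after only by way of photos |
| Patient preference | Not listed | Not listed | Listed at 0 of 2 visits |

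The schedule has 3 instruments x 2 times x 2 visits = 12 pain scores per patient. The synopsis names only the VAS for this endpoint, so the scores that matter are the 2 post-procedure VAS scores.

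**2. Is absence from the schedule evidence of absence?** The synopsis plans the incidence of adverse events, yet no visit step mentions them. The schedule is therefore not a complete list of what is recorded.

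**3. The SAP's sample size.** The figure of 22 cannot be reproduced, because no mean, SD or correlation is given. Solving backwards for a paired t-test (n = 22, 80% power, two-sided 0.05, noncentral t) gives a standardised paired difference of 0.626. For a 50% reduction, the SD of the paired difference is then 0.5 / 0.626 = 0.80 of the reference mean. That is plausible, but it does not show which pain score was meant.

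**4. What turns on post score versus change.** Let f = mean pre-procedure VAS / mean sharp post-procedure VAS, with equal pre-procedure means at both sessions. The documents give no value for f; 0 to 0.5 is an assumed range.

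- A 50% lower laser post score reduces the change by 0.5 / (1 - f).
- A 50% smaller laser change reduces the post score by 0.5 x (1 - f).

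| f | Reduction in change if post score is 50% lower | Reduction in post score if change is 50% smaller |
|---|---|---|
| 0 | 50% | 50% |
| 0.25 | 66.7% | 37.5% |
| 0.5 | 100% | 25% |

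If f is 1 or more, a percentage reduction in the increase is undefined.

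The percentages differ, but the absolute laser-sharp difference does not. Difference in changes = (laser post - sharp post) - (laser pre - sharp pre), and the last bracket averages zero under the equal-means assumption. With f = 0.25 and sharp post set at 100, pre is 25. A laser post score of 50 gives changes of 75 and 25, which differ by 50, as do the post scores.

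Precision can move either way. Suppose 22 was sized for the post score, pre and post SDs are equal, and the pre and post treatment differences correlate at rho. The change score's variance is then 2(1 - rho) times that of the post score. Power with 22 patients would be about 51%, 63%, 80% and 98% at rho = 0, 0.25, 0.5 and 0.75. The documents do not give rho.

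**5. Which score do the documents point to?** Within one sentence the SAP writes size and bacterial load as before-and-after quantities and pain as one quantity tied to the procedure. The synopsis calls it procedural pain by VAS, compared between modalities. The post-procedure VAS fits both descriptions; a change score fits neither well.

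**6. The 3x2 table.** Preference (laser, sharp, none) is one candidate. Bleeding is another: it is a secondary endpoint, is assessed at both visits, and could be graded in three levels by two modalities. The SAP's list says what the variables include, so leaving bleeding out of it settles nothing.

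**The case for a change.** The strongest case for a change is that it would be cheap and the loss could be permanent. One preference question at the end of week two and one clause in the VAS wording would remove the doubt. Identical wording of the pain step before and after debridement supports a current-pain reading as easily as a procedural one. A variable that sizes the study deserves an explicit definition.

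Part of this stands. The VAS reference period is unstated, and a report should say what patients were asked. Satisfaction is not preference, and its instrument and timing are missing.

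The rest carries less weight. The between-treatment contrast is stated in the synopsis. Anesthetic is applied at both sessions, so if its use is similar, its effect largely cancels in the within-patient comparison; the post score follows anesthetic too. The cheap remedies work only while visits remain. The protocol is dated November 2015 with an expected duration of six weeks, and the SAP is dated February 2018 and refers to its tests partly in the past tense. Neither document says whether visits were finished. For size, photo-based measurement would need a scale in the images, which the documents do not mention; but size is not a protocol endpoint.

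**Conclusion.** The mismatches are correctly read, but they are missing detail rather than an error in the plan. Preference is unlisted at both visits, the post-procedure VAS has no stated reference period, and size after debridement has photos without a stated method. All three concern secondary or other variables. The primary endpoint, bioburden, has biopsies before and after at both visits.

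A study team working from the synopsis and the SAP would fill these gaps sensibly: take the post-procedure VAS as procedural pain, compare laser with sharp within patient by the planned paired t-test, apply the Fisher test to whichever categorical item was recorded, and report any listed variable that was not obtained. No stated rule or figure is shown to give a wrong result. The spread of 25% to 50% in what a halved change would mean for the post score depends on an assumed f and on the less natural reading of the SAP.

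This conclusion assumes that the schedule is not exhaustive, which its silence on adverse events supports, and that the SAP's contrast between pain and the before-and-after variables is deliberate. If preference was in fact never asked, that is a matter for disclosure in the report; it would not alter the primary analysis.

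### The SAP's paired t-test for pain gives no role to the pre-debridement VAS scheduled at both visits: a possible loss of precision, not a bias

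*SAP*

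**What the plan says.** **Pain variable.** The SAP (Methods) states: "Analysis variables include pain during debridement, pre- and post-debridement wound sizes, pre- and post-debridement bacterial loads, and patient preference". Wound size and bacterial load are named as before-and-after quantities; pain is not.

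**Test.** The SAP (Statistical Analysis) states: "A paired t-test was planned to evaluate continuous data". It names no covariate, baseline or period term.

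**Power.** The SAP states: "The a priori power analysis presumes a 50% reduction in patient-reported pain", and then: "A sample size of 22 patients would be required to achieve 80% power", two-sided at 0.05. No other outcome has a power statement.

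**Data collected.** Under the pre-procedure step of both visits, the protocol (Study Schedule, weeks one and two) has: "Record VAS pain score, Present Pain Intensity, and Brief Pain Inventory". The same line appears after the procedure. Between the pre-score and the procedure comes the step "Apply anesthetic".

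**Status of pain.** In the protocol synopsis pain is a secondary endpoint: "Comparison of the procedural pain from the two treatment modalities as determined by subject reported visual analog scale (VAS) pain scores". Neither document says what the pre-procedure scores are for.

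**The concern.** A paired comparison cancels whatever is constant in a patient across the two visits. Resting pain in a chronic ulcer need not be constant over a week. If a patient arrives in more pain at the laser visit than at the sharp visit, that gap can feed into the laser-minus-sharp difference in procedural pain. The trial measures the gap at both visits, but the planned analysis does not use it.

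At stake is the precision of the pain comparison in a trial of about 20 patients, on the one outcome the SAP powers. Adjusting for a prognostic covariate that is already collected is one of the few ways to gain precision without more patients.

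**Working it through.** **Inputs from the documents.** Two-sided α = 0.05, power 80% and N = 22 (SAP, Statistical Analysis); N = 20 (protocol synopsis).

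**Assumptions.** The SAP's calculation was for a paired t-test. r is the correlation, across patients, between the laser-minus-sharp difference in pre-debridement VAS and the laser-minus-sharp difference in procedural VAS.

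**Step 1: the plan's own figure.** The 22 cannot be reproduced forward, because the SAP gives no mean, no SD and no within-patient correlation. Solving the noncentral t backward (df = 21, critical value 2.080) gives a standardised paired difference dz = 0.626, that is, a noncentrality of 0.626 × √22 = 2.94. With a 50% reduction, the SD of the paired difference would be 0.5/0.626 = 0.80 of the reference mean pain. If the calculation was instead a two-sample one, the implied effect would be 1.26 (11 per group) or 0.86 (22 per group), and the power figures below would not apply.

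**Step 2: adjusted analysis.** Regress the difference in procedural VAS on the difference in pre-VAS and test the intercept. The residual variance is multiplied by (1 − r²). Estimating the slope inflates the variance of the intercept by (N − 2)/(N − 3) on average. The noncentrality is therefore

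dz × √N / √[(1 − r²)(N − 2)/(N − 3)], with N − 2 degrees of freedom.

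Example at N = 22, r = 0.5: 2.938 / √(0.75 × 20/19) = 3.31, against a critical value of 2.086, which gives power 88%.

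| Analysis | N = 22 | N = 20 |
|---|---|---|
| Unadjusted paired t-test | 80% | 76% |
| Adjusted, r = 0 | 78% | 73% |
| Adjusted, r = 0.2 | 79% | 75% |
| Adjusted, r = 0.3 | 81–82% | 77% |
| Adjusted, r = 0.4 | 84% | 80% |
| Adjusted, r = 0.5 | 88% | 84% |

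At N = 22 the adjusted and unadjusted analyses have equal power near r = 0.23.

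**Step 3: adding the period effect.** In laser-first patients the laser-minus-sharp difference contains the treatment effect plus the week-one-minus-week-two effect. In sharp-first patients it contains the treatment effect minus that same quantity. A sequence indicator coded +1 and −1 therefore absorbs the period effect, and the intercept remains the treatment effect. Simulating this model at N = 22 with 11 patients per sequence (20,000 trials per setting, normal data, dz = 0.626) gave power of 78%, 81% and 88% at r = 0, 0.3 and 0.5. The extra term costs almost nothing.

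**Step 4: why not a change score.** Subtracting the pre-score multiplies the variance of the difference by 1 + k² − 2rk, where k is the ratio of the SD of the pre-score difference to that of the procedural difference. With k = 1 and r = 0.3 the factor is 1.4, and power at N = 22 falls to 66%. With k = 1 it only breaks even at r = 0.5. Regression lets the data set the slope.

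**The case against.** **The test is valid as it stands.** A paired t-test is a standard crossover analysis. A reader might infer that differences in starting pain between a patient's laser and sharp visits bias the pain contrast. The documents do not support that: both describe a randomised crossover, so, with balanced sequences and no carryover, shifts in resting pain fall on either treatment by chance. A chance imbalance in this small sample is the same noise that already sits in the standard error, not a second problem. This objection stands in full and limits the point to precision.

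**The gain is unknown.** It rests entirely on r, which the documents do not give. Anesthetic is applied after the pre-score and may weaken the link between resting and procedural pain. Below about r = 0.23 adjustment loses a little power. This also stands.

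**That pain is analysed without its baseline is an inference.** The SAP's list is introduced by a verb that need not be exhaustive, and no scoring rule is given. The protocol schedules scores before and after debridement but none during it, so the variable could be the post-procedure score, a change or an unscheduled rating. This stands as a caution. Under any of these readings the SAP leaves the role of the pre-score unstated.

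**The week-two pre-score follows the first treatment by one week.** If laser and sharp leave different resting pain, the covariate carries part of the first treatment's effect. Adjustment does not remove the week-two treatment's own effect, because the score precedes it, but the adjusted estimate is not free of carryover. Nor is the unadjusted one. This is a reason to report both.

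**Pain is secondary in the protocol, in a study it calls a pilot.** True. The point concerns the comparison the SAP powers, not the protocol's primary endpoint of bioburden.

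**Conclusion.** The point holds as a possible loss of precision in the pain comparison. The SAP assigns no role to a pre-debridement VAS that the protocol schedules at both visits. It does not hold as a claim of bias or of an invalid test.

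The size is bounded below but otherwise uncertain: at N = 22, about 2 points of power lost if the pre-score is uninformative, 1 to 2 points gained at r = 0.3 and 8 points at r = 0.5. At the protocol's 20 patients, r of about 0.4 would bring the 76% of the unadjusted test back to about 80%. All these figures rest on reading the SAP's 22 and 80% as a paired t-test and on an assumed r. The change is cheap and worth making, but no particular gain can be promised from these documents.

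**What to change.** In the SAP's Statistical Analysis section:

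1. State which recorded VAS score is the procedural pain variable.
2. For that variable, specify a regression of the within-patient laser-minus-sharp difference in procedural VAS on the laser-minus-sharp difference in same-visit pre-debridement VAS plus a sequence indicator coded ±1. The intercept is the treatment effect; the sequence coefficient takes up the period effect.
3. If a mixed model is preferred, centre the pre-VAS within patient or use fixed patient effects. A random-intercept model with the uncentred visit-specific pre-VAS is not the same analysis, because its slope blends between-patient and within-patient information.
4. Keep the unadjusted paired t-test as a sensitivity analysis and report the two side by side. Do not substitute a simple change score.

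The cost is a few sentences and no new data. The statistical price is two degrees of freedom (one without the sequence term) and about 2 points of power if the baseline is uninformative. Because the week-two pre-VAS may carry some effect of the first treatment, the adjusted result should be read beside the unadjusted one.
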